10.4 Physical Examination

A general physical examination should include general appearance and the following body systems need to be examined: lymph nodes, mouth and throat (non-tumor bearing parts), lungs, cardiovascular system, abdomen, extremities, musculoskeletal system, neurological system and skin (for assessment of skin reactions refer to Section 10.12). The outcome of the physical examination must be recorded in the eCRF.

10.5 Vital Signs

Vital signs should be recorded in the eCRF including temperature, blood pressure and heart rate. Within each visit, preferably the same equipment shall be used for vital signs measurements. Vital signs should be assessed just before and no longer than 30 minutes before infusion start, during and after the infusions until two hours after the infusions, as follows:

Final 5.0 (incorporating Protocol Amendment 4) 06 Jul 2017

Vital signs assessments during the Dose Escalation Part

Cycle 1	Cycle 2 – Cycle 12	
Pre-infusion (including weight)	Pre-infusion (including weight)	
30 min after start of infusion (± 5 min)		
At the end of infusion (± 5 min)	At the end of infusion (± 5 min)	
30 min after end of infusion (± 5 min)		
1 hour after end of infusion (± 5 min)		
2 hours after end of infusion (± 15 min)	2 hours after end of infusion (± 15 min)	

If the infusion lasts for more than 30 minutes, vital signs should be assessed approximately every 30 minutes (\pm 5 minutes) for the duration of infusion.

Vital Signs Assessments during the Cohort Expansion Part

Cycle 1 – Cycle 9
Pre-infusion (including weight)
At the end of infusion (± 5 min)
2 hours after end of infusion (± 15 min)
On non-infusion visits, to be performed in relation with other assessments.

10.6 Electrocardiogram

Electrocardiograms will be recorded digitally at the sites by using the standard 12-leads. One ECG will be performed at screening. Three ECGs should be performed at least two minutes apart before the first infusion of the trial drug in each cycle, in accordance with the ECG Specifications Manual. The digital ECGs will be transmitted from the sites electronically to a central laboratory for measurement of the cardiac intervals and morphologic assessment by a central cardiologist.

An overall interpretation of the ECGs will be performed by the investigator, or the investigator may delegate this task to a cardiologist, if applicable.

For the ECG recordings, the patients must be resting in a supine position for at least 10 minutes. Any irregularity observed or occurring during the ECGs (e.g., vomiting, cough) should either result in a repeat of the ECG or be annotated on the eCRF with the description and time of the occurrence.

10.7 Computerized Tomography

All patients will have a CT-scan with contrast of thorax, abdomen and pelvis performed during screening. If there is suggestion of brain metastases/tumors, a CT-scan of the head will be performed before inclusion.

Up to five target lesions (maximum two per organ) will be defined at screening and these must be followed throughout the trial. Non-target lesions will also be assessed throughout the trial.

Final 5.0 (incorporating Protocol Amendment 4) 06 Jul 2017

Scans will be repeated every six weeks (at the end of every second cycle) during the trial period. If the result is PR or better, CT-scan should be repeated after four weeks to confirm response. CT-scans can be performed up to seven days before Day 1 of the relevant cycle to ensure results are available before subsequent dosing.

Additional CT-scans may be performed at the investigators' discretion to confirm response or new symptoms. In this case, the investigator must choose the imaging technology based on the clinical indication.

Magnetic resonance imaging can be performed instead of a CT-scan if the patient is allergic to iodine contrast or at the discretion of the investigator, after approval of the sponsor.

The reading of the surveys will be done by a radiologist. Sites should attempt to maintain the same radiologist throughout the trial. The overall interpretation of the evaluation shall be recorded in the eCRF and a copy of the evaluation reports should be kept in the patient's file.

10.8 ECOG Performance Status

The ECOG performance status scale (Appendix 1) will be used and will be assessed by the investigator at screening, on Day 1 of each cycle, and at the EOT Visit.

10.9 Adverse Events

Adverse events will be assessed and reported at each visit. All AEs will be graded according to the NCI-CTCAE version 4.03 (NCI-CTCAE v4.03, 2010).

SAEs and non-serious grade 3 AEs will be reported from the investigational site to the sponsor within 24 hours. In addition, all non-serious grade 2 ocular AEs must be reported from the investigational site to the sponsor within 24 hours.

Weekly Safety/Medical meetings will be held in the Dose Escalation part of the trial to evaluate all AEs and laboratory data and follow-up information obtained during the previous week. In the Cohort Expansion part of the trial, bi-weekly evaluations will be made.

Further details on AEs monitoring and reporting are provided in Section 11.

10.10 Concomitant Medication

Any medication or therapy other than the trial drug is considered concomitant medication and should be recorded in the eCRF with the following information:

- Start date.
- Route of administration.
- Stop date of administration or ongoing at trial termination.
- Indication/reason for use.

The total daily dose should be provided whenever possible.

The recording period for concomitant medication will start from Visit 0 (Screening) until the EOT Visit.

Final 5.0 (incorporating Protocol Amendment 4) 06 Jul 2017

10.11 Bleeding Assessments

Major bleeding is defined as any of the following conditions according to the International Society on Thrombosis and Haemostasis (Shulman and Kearon, 2005):

- Fatal bleeding; and/or
- Symptomatic bleeding in critical area organ, such as intracranial, intraocular, retroperitoneal, intra-articular or pericardial, or intramuscular with compartment syndrome; and/or
- Bleeding causing a drop in hemoglobin level of 20 g/L (1.24 mmol/L) or more, or bleeding leading to transfusion of two or more units of whole blood or red cells.

Minor bleeding includes:

• Cutaneous bleeding, nose bleeding, oral cavity bleeding, menorrhagia, spontaneous muscle hematomas without compartment syndrome, grade 1 and 2 hematuria, and excessive bleeding after minor injury.

Any bleeding AE shall also be recorded with a CTCAE grading.

10.12 Skin Assessments

Development of skin reactions will be monitored during the trial and registered on a separate form. A Dermatologist must be available for consulting at each site.

Rash should be reported and graded according to the NCI-CTCAE for macular-papular skin rash according to Table 8 below:

Table 8: Grading of Skin Rash

System Organ Class	Event	Grade 1	Grade 2	Grade 3	Grade 4	Grade 5
Skin and subcutaneou s tissue disorders	Rash maculo- papular	Macules/pap ules covering < 10% BSA with or without symptoms (e.g., pruritus, burning, tightness)	Macules/pap ules covering 10-30% BSA with or without symptoms (e.g., pruritus, burning, tightness); limiting instrumental activities of daily living	Macules/pap ules covering > 30% BSA with or without associated symptoms; limiting self-care activities of daily living	Life- threatening	Death

BSA=Body Surface Area

In case of bulla/bullae, these should be measured and reported as AEs.

Final 5.0 (incorporating Protocol Amendment 4) 06 Jul 2017

Patients should be withdrawn if they experience a trial drug-related grade ≥ 3 macular-papular skin rash (covering $\geq 30\%$ of BSA), bullae (skin blisters ≥ 0.5 cm) or TEN, Steven Johnson or grade ≥ 3 cutaneous vasculitis.

10.13 Neuropathy Assessment

A standard scheme for assessment of peripheral neuropathy will be used and will be included in the eCRF to obtain information on whether potential neuropathy is peripheral or central, motor or sensory, and the localization.

10.14 Ophthalmological Evaluation

Ophthalmological evaluations should be performed at baseline and during the trial as indicated in the trial flow chart.

The ophthalmological evaluation should include collection of medical ophthalmological history (at baseline only), visual acuity assessment, Shirmer's test, slit-lamp examination, measurement of ocular pressure and funduscopic.

Patients experiencing ocular symptoms during the trial must be referred to an ophthalmologist for prompt review (preferably within 72 hours and no later than within one week).

10.15 Radionuclide Bone Scan

For patients with CRPC, a radionuclide bone scan will be performed at screening, every 12 weeks during treatment (i.e., Day 1 of Cycles 5 and 9), and upon clinical indication. If there is suspicion of progression, another bone scan will be performed 12 weeks later. The screening radionuclide bone scan can be performed up to four weeks prior to Visit C1-V1.

10.16 Laboratory Assessments

Blood sampling will be collected for assessment of laboratory parameters. Some laboratory samples will be tested at the site while others will be drawn and shipped for centralized testing.

A manual with detailed description of the procedures for sampling, handling, storage and shipment of the laboratory samples and all material such as test tubes and labels for central analysis will be provided by the central laboratory. The manual and the result reports will include all reference ranges.

Laboratory equipment in central and local laboratories may provide standard analyses not requested in the protocol but produced automatically in connection with the requested analyses. Such data will not be transferred to the eCRF but must be reported to the investigator.

If a non-serious grade ≥ 3 laboratory abnormality occurs during Cycle 1 and is assessed as related or possibly related to the trial drug, then a new laboratory sample should be collected performed within 48 hours (and as close to 48 hours as possible) and reported as an unscheduled visit. This is to confirm or reject the fulfillment of the DLT assessment as defined in Section 8.4.8 (Any grade ≥ 3 non-hematological AEs which occur during the first treatment cycle and are at least possibly trial drug related, excluding non-hematological laboratory abnormalities that have no clinical consequences and resolve within 48 hours).

Final 5.0 (incorporating Protocol Amendment 4)

A patient can always be called in for an unscheduled visit(s) if judged necessary by the investigator.

To monitor patient safety, the investigator can request additional blood samples at the unscheduled visit. The reason for the visit and visit date must be recorded in the eCRF.

10.16.1 Hematology

In the Dose Escalation part of the trial, hematology parameters will be analyzed at the site laboratory.

In the Cohort Expansion part of the trial, hematology parameters will be analyzed at a central laboratory.

A blood sample will be drawn at each visit for analysis of the following parameters: red blood cell count, hemoglobin, hematocrit, mean corpuscular volume, mean corpuscular hemoglobin, mean corpuscular hemoglobin concentration, white blood cell count with differential, platelet count and reticulocyte count.

10.16.2 Biochemistry

In the Dose Escalation part of the trial, biochemistry parameters will be analyzed at the site laboratory.

In the Cohort Expansion part of the trial, biochemistry parameters will be analyzed at a central laboratory.

A blood sample will be drawn at each visit for analysis of the following parameters: sodium, potassium, calcium, magnesium, creatinine, blood urea nitrogen, AST, ALT, alkaline phosphatase, albumin, glucose, total creatine kinase, total bilirubin, lactate dehydrogenase, uric acid, s-ferritin, C-reactive protein and glycosylated hemoglobin.

10.16.3 Coagulation Factors

In the Dose Escalation part of the trial, coagulation factors will be analyzed at the site.

In the Cohort Expansion part of the trial, coagulation factors will be analyzed at a central laboratory.

Samples will be taken for analysis of PT, INR, aPTT, D-dimer and fibrinogen.

10.16.4 PSA and CA 125

For patients with CRPC in the Dose Escalation part of the trial, blood samples for PSA assessment will be drawn for local analysis.

For patients with ovarian and endometrial cancer:

- In the Dose Escalation part of the trial, blood samples for CA 125 assessment will be drawn for local analysis.
- In the Cohort Expansion part of the trial, blood samples for CA 125 assessment will be analyzed at a central laboratory.

Final 5.0 (incorporating Protocol Amendment 4)
06 Jul 2017

10.16.5 Flow Cytometry

A blood sample will be drawn for central analysis of flow cytometry of the following:

Total T-cells (CD3⁺), helper T-cells (CD3⁺CD4⁺), cytotoxic T-cells (CD3⁺CD8⁺), NK-cells (CD3⁻CD56⁺CD16⁺) and B-cells (CD45⁺CD19⁺).

Additional flow cytometry subgroups may be added based on findings.

10.16.6 Pregnancy Test

A blood sample will be drawn at the Screening Visit and at Day 1 of each cycle from all women of childbearing potential and will be analyzed at the site laboratory in the Dose Escalation part of the trial.

Pregnant women may not take part in this trial and will be considered as screening failures. A serum pregnancy test will also be performed during the Follow-up period visits and at the EOT Visit.

In order to be considered as sterilized or infertile, a patient must have undergone surgical sterilization (vasectomy/bilateral tubectomy; hysterectomy and bilateral ovariectomy) or be postmenopausal (twelve months or more with no period prior to enrollment).

Safe hormonal contraceptives include contraceptive pills, implants, transdermal patches, hormonal vaginal devices or injections with prolonged release.

In the Cohort Expansion part of the trial, pregnancy tests will be analyzed at a central laboratory.

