- ⁷ Signs and symptoms occurring between Visit 0 and first infusion should be recorded as medical history (see Section 10.2 for details). SAEs should be reported as of the signing of the informed consent.
- ⁸ Height is only assessed at the Screening Visit. During the trial, only body weight is measured on the first dosing day in a cycle, as part of the dose calculation. If body weight is assessed ≤ 7 days before the first day of the planned dosing in a cycle, this value can be used to calculate dose.
- ⁹ Temperature, blood pressure and heart rate. Within each visit, preferably the same equipment shall be used for vital signs measurements. Vital signs should be assessed just before and no longer than 30 minutes before infusion start, during and after the infusions until 2 hours after end of infusions, as indicated in Section 10.5.
- ¹⁰ Optional.
- ¹¹ One ECG will be performed at screening. Three ECGs should be performed at least 2 minutes apart before infusion of the trial drug on Visit 1 for all cycles, in accordance with the ECG Specifications Manual.

Footnotes to Trial Flowchart: Dose Escalation Part

¹² Within 4 weeks prior to Visit C1-V1. All patients will have a CT-scan with contrast of thorax, abdomen and pelvis performed as part of the screening procedure. If a CT-scan has been performed within 4 weeks prior to Visit C1-V1 as part of standard procedure, it is acceptable as screening CT-scan for the trial. If there is suggestion of brain metastases/tumors, a CT-scan of the head will be performed before inclusion.

¹³ At the end of every second cycle, i.e., on Day 1 of Cycles 3, 5, 7, 9 and 11, CT-scans can be performed up to 7 days before Day 1 of the relevant cycle to ensure result to be available before subsequent dosing. Additional scans on 21 days (± 7 days) after Day 15 of Cycle 12, and at the EOT Visit. To be completed as indicated to confirm response, new symptoms, end of trial or physician discretion.

¹⁴ Radionuclide bone scan and PSA will be performed for CRPC patients. Radionuclide bone scan will be performed at screening, every 16 weeks (i.e., Day 1 of Cycles 5 and 9), and upon clinical indication. If there is suspicion of progression, another bone scan will be performed 12 weeks later. The screening radionuclide bone scan can be performed up to 4 weeks prior to Visit C1-V1.

15 Hematology, biochemistry, serology and pregnancy test will be analyzed locally at the sites. All other laboratory parameters will be analyzed centrally.

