Treatment Cycle	Screening		Cycle 1			Cycle 2-9		EOT ¹	Withdrawal Safety Follow-up ²	Unscheduled
Visit Number	0	1^3	2	3	13	2	3	-	-	1-X
Day/Week	≤21 days prior to Visit C1-V1	1d	8d	15d	1d	8d	15d	-	30 days after last dosing	-
Visit window ⁴		-	±1d	±1d	±3d	±1d	±1d	-	±14d	-
PSA ¹⁴	X	X			X			X		X^{10}
CA 125 ¹⁶	X	X			X			X		X ¹⁰
Flow Cytometry		X^{17}			X ¹⁷			X		X^{10}
Pregnancy Test	X	X			X			X		X^{10}
ADA (Immunogenicity)	X	X			X					X^{10}
Hepatitis B, C, CMV, HPV ¹⁸	X							X		X^{10}
PK Sampling ¹⁹	X	X	X	X	X	X	X			X^{10}
Tumor biopsy	X^{20}									X^{10}
Biomarker	X						X^{21}			

Abbreviations: ADA=anti-drug antibody; CMV=cytomegalovirus; CRPC=Castration-resistant prostate cancer; CT=computerized tomography; ECG=electrocardiogram; ECOG=Eastern Cooperative Oncology Group; EOT=End of Trial; HBc=Hepatitis B core; HBs=Hepatitis B surface; HBsAg=Hepatitis B surface antigen; HCV=hepatitis C virus; HPV= human papilloma virus; Ig=Immunoglobulin; PCR=polymerase chain reaction; PD=progressive disease; PK=pharmacokinetic; PSA=prostate specific antigen; SAE=serious adverse event

Footnotes to Trial Flowchart: Cohort Expansion Part

¹ If the patient shows PD, is to start new anti-cancer treatment or withdraws from trial due to another reason during treatment, the EOT Visit should be performed as soon as possible after decision of withdrawal.

²Only SAEs will be assessed.

³ The patient shall stay at hospital for at least 2 hours after the infusion and may be requested to stay longer at the discretion of the investigator.

⁴ The specified visit windows are in accordance with the previous visit. Visit 1 of Cycle 2 and onwards should be performed 7 days ± 3 days after Day 15 of the previous cycle.

⁵ Informed consent must be obtained before or at the Screening Visit window i.e., may be reasonably prior to the screening date.

⁶ Signs and symptoms occurring between Visit 0 and first infusion should be recorded as medical history (see Section 10 for details). SAEs should be reported as of the signing of the informed consent.

⁷ Height is only assessed at the Screening Visit. During the trial, only body weight is measured on the first dosing day in a cycle, as part of the dose calculation. If body weight is assessed \leq 7days before the first day of the planned dosing in a cycle, this value can be used to calculate dose.

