⁸ Temperature, blood pressure and heart rate. Within each visit, preferably the same equipment shall be used for vital signs measurements. Vital signs should be assessed just before and no longer than 30 minutes before infusion start, during and after the infusions until 2 hours after end of infusions, as indicated in Section 10.5.

⁹ Optional.

Footnotes to Trial Flowchart: Cohort Expansion Part

¹⁰ One ECG will be performed at screening. Three ECGs should be performed at least 2 minutes apart before infusion of the trial drug on Visit 1 for all cycles, in accordance with the ECG Specifications Manual.

Within 4 weeks prior to Visit C1-V1. All patients will have a CT-scan with contrast of thorax, abdomen and pelvis performed as part of the screening procedure. If a CT-scan has been performed within 4 weeks prior to Visit C1-V1 as part of standard procedure, it is acceptable as screening CT-scan for the trial. If there is suggestion of brain metastases/tumors, a CT-scan of the head will be performed before inclusion.

¹² At the end of every second cycle, i.e., on Day 1 of Cycles 3, 5, 7 and 9, CT-scans can be performed up to 7 days before Day 1 of the relevant cycle to ensure result to be available before subsequent dosing. Additional scan at the EOT Visit. To be completed as indicated to confirm response, new symptoms, end of trial or physician discretion.

¹³ Patients experiencing ocular symptoms must be referred to an ophthalmologist for prompt review (preferably within 72 hours and no later than within one week).

¹⁴ Radionuclide bone scan and PSA will be performed for CRPC patients. Radionuclide bone scan will be performed at screening, every 16 weeks (i.e., Day 1 of Cycles 5 and 9), and upon clinical indication. If there is suspicion of progression, another bone scan will be performed 12 weeks later. The screening radionuclide bone scan can be performed up to 4 weeks prior to Visit C1-V1.

¹⁵ Laboratory parameters will be analyzed centrally.

¹⁶ For patients with ovarian and endometrial cancer.

¹⁷ Flow cytometry only on Cycle 1 and Cycle 5.

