8.1.1.2 Treatment Phase (C1 to CX)

Dose Escalation Part

The investigator must have evaluated the patient's eligibility and confirm receipt of sponsor decision and patient number before the patient's first infusion.

Tisotumab vedotin (HuMax-TF-ADC) will be administered on Days 1, 8 and 15 of a 28-day cycle. Dose escalation to MTD is anticipated to involve up to three dose levels with an anticipated maximum dose level of 1.5 mg/kg.

Patients will receive four cycles (each with three doses) of tisotumab vedotin (HuMax-TF-ADC) at 28-day intervals. Thus, the treatment period will last for 16 weeks or until the patient withdraws from the treatment/trial due to the withdrawal criteria.

After four cycles, if there is evidence of the patient benefitting from treatment, at the discretion of the treating physician, there is an option to continue in the trial for up to a maximum of eight additional cycles (32 weeks) or until the patient withdraws from the treatment/trial due to the withdrawal criteria.

The treatment period will have a maximum duration of 48 weeks.

Cohort Expansion Part

The investigator must have evaluated the patient's eligibility before the patient's first infusion.

Tisotumab vedotin (HuMax-TF-ADC) will be administered on Day 1, 8 and 15 of a 28-day cycle. Twenty to 30 patients will receive up to nine cycles of three doses of HuMax-TF-ADC at the dose determined by the sponsor in agreement with the DMC based on the Dose Escalation part of the trial.

Severe ocular toxicity has been observed at 1.2 mg/kg 3q4wk. Patients will no further receive the 3q4wk schedule; instead tisotumab vedotin (HuMax-TF-ADC) 2.0 mg/kg will be administered once q3wk, on Day 1 of each 21-day cycle, regardless of the prior dose(s) administered. The next dose of tisotumab vedotin cannot be administered until at least 21 days have elapsed since the last administration.

Final 5.0 (incorporating Protocol Amendment 4) 06 Jul 2017

The treatment period will last for up to 36 weeks (or less after changing to the once q3wk dosing scheme) or until unacceptable toxicity or disease progression at the discretion of the treating physician.

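### In the Cohort Expansion part the Day 1 pregnancy test goes to a central laboratory while drug is given at the same visit, and nothing requires the result to be seen before infusion

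*Protocol*

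**What the plan says.** Section 10.16.6 has the pregnancy sample "drawn at the Screening Visit and at Day 1 of each cycle from all women of childbearing potential". The two parts of the trial then differ in where it is read.

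- **Dose Escalation.** Section 10.16.6 names the site laboratory, and Table 1 footnote 15 agrees: "Hematology, biochemistry, serology and pregnancy test will be analyzed locally at the sites".
- **Cohort Expansion.** Section 10.16.6 states: "In the Cohort Expansion part of the trial, pregnancy tests will be analyzed at a central laboratory". Table 5, the current flow chart, repeats this in footnote 15 without exempting any test: "Laboratory parameters will be analyzed centrally".

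Dosing falls on the same day as the sample. Under Section 8.1.1.2, "2.0 mg/kg will be administered once q3wk, on Day 1 of each 21-day cycle", and "The next dose of tisotumab vedotin cannot be administered until at least 21 days have elapsed since the last administration". Table 5 marks drug administration and the pregnancy test in the same Day 1 column, and shows no pregnancy test at Day 8 or Day 15.

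For imaging, the protocol does provide for the result to precede the dose. Table 5 footnote 12 says: "CT-scans can be performed up to 7 days before Day 1 of the relevant cycle to ensure result to be available before subsequent dosing". The pregnancy sample has no such provision.

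**The concern.** A pregnancy test repeated every cycle can spare a patient the next dose only if it is read before that dose. In Dose Escalation a site-read result could be known at the visit. In Cohort Expansion the sample is shipped, and a site can follow the protocol to the letter while infusing before the result exists.

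The protocol itself treats pregnancy as a reason to stop at once: it is a criterion for withdrawal from treatment (8.3.4.1), and 11.4.2.3 calls for that withdrawal without delay. Contraception is required for six months beyond the last infusion (8.3.1, criterion 11). What is at stake is an avoidable further dose of a cytotoxic conjugate in a patient whose sample of that day would have been positive. No endpoint or safety analysis is at stake.

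**Working it through.** The protocol states no figure for the age of the pregnancy result at dosing, so there is none to reproduce. It can be built from the visit schedule.

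**Inputs**

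- Table 5: Day 8 and Day 15 visits each have a window of ±1 day.
- Table 5 footnote 4: windows count from the preceding visit, and "Visit 1 of Cycle 2 and onwards should be performed 7 days ± 3 days after Day 15 of the previous cycle".
- Section 8.1.1.2: at least 21 days between doses.
- Table 5: nine cycles.
- Section 9.2.1: screening procedures no more than 21 days before the first dose.
- Assumption, not in the protocol: the central result does not return on the day of sampling.

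**Interval between successive Day 1 visits**

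- Day 1 to Day 8: 7 ± 1 = 6 to 8 days
- Day 8 to Day 15: 7 ± 1 = 6 to 8 days
- Day 15 to next Day 1: 7 ± 3 = 4 to 10 days
- Sum: 6 + 6 + 4 = 16 days up to 8 + 8 + 10 = 26 days
- With the dosing minimum: max(16, 21) = 21, so **21 to 26 days**

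No pregnancy test is scheduled in between, so this is the age of the last scheduled result in hand at each dose. Narrower readings change little: 21 to 25 days if the Day 8 and Day 15 windows do not accumulate, and 21 to 24 days if only the ±3 days on Day 1 counts.

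**Dose holds.** If the sample is taken only at the delayed Day 1 visit, a two-week hold gives up to 26 + 14 = 40 days. An ocular hold at the 12-week limit in 8.4.5.3 gives up to 26 + 84 = 110 days.

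**Dosing occasions.** Cycle 1 is gated by the negative screening test, at most 21 days old. That leaves 9 − 1 = 8 occasions per woman (Cycles 2 to 9).

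**Extra exposure per pregnancy.** The next dose is at least 21 days away. If the result returns within that time, a positive Day 1 sample is followed by one dose, the one given that day, before withdrawal. If the result takes longer than a cycle, more than one dose could follow.

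**Why this test differs from hematology and biochemistry.** Those are also central, but Table 5 draws them at Days 8 and 15 too. Day 15 falls at most 8 + 8 = 16 days after Day 1. With the 21-day minimum, the Day 15 sample therefore precedes the next dose by 21 − 16 = 5 to 10 days, against 21 to 26 days for the pregnancy test.

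**After the change.** A site test read on Day 1 before infusion is 0 days old. An early-draw window of up to 7 days with review before dosing would give 0 to 7 days.

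**The case against.** **Local testing is foreseen elsewhere.** Section 10.16 says that some samples are tested at the site, and 12.5.2 says that some assessments are run locally around the infusion for patient safety. Neither names the pregnancy test, and 10.16.6 does, assigning it to the central laboratory. The specific rule governs. The general sentences show only that a local test would not be foreign to the protocol.

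**The turnaround time is unknown.** This stands. If the central laboratory reported the same day and sites waited, the gap would close in practice. The protocol promises neither. The laboratory manual is not available here; 10.16 describes it as covering sample procedures and reference ranges, so a check before dosing inside it can be neither confirmed nor excluded.

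**The safeguards are substantial.** This also stands. Entry requires a negative serum test and contraception is mandatory. A patient whose status changes before the first dose is excluded (8.3.1), and the investigator may order extra samples (9.2.3), though only at discretion. A pregnancy conceived on treatment has already followed an earlier dose, so the delay adds to an existing exposure.

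**A stronger reading is tempting.** A reader might infer up to eight unprotected doses per woman. The documents do not support that. Eight counts dosing occasions; once a positive result arrives, withdrawal is immediate, and the likely increment is about one dose per pregnancy. Nor does the protocol forbid a local test or instruct sites to dose before the result is known. It only fails to prevent it.

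**Conclusion.** The point holds as a minor gap in a visit procedure that the protocol itself fixes. In Cohort Expansion the Day 1 pregnancy test can be read after the dose given that day. On schedule, the last scheduled result in hand at each Cycle 2 to 9 dose is then 21 to 26 days old, and older after a hold. The likely consequence is one further dose before a pregnancy is acted on.

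This rests on one assumption, that the central result does not return the same day. That is reasonable for a shipped sample but is not stated in the protocol. The number of women of childbearing potential is not given, so the expected number of affected patients cannot be calculated. Cycle 1 lies outside the 21 to 26 day figure because the screening test gates it.

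**What to change.** In Section 10.16.6 and Table 5 footnote 15, state that in the Cohort Expansion part the Day 1 pregnancy test for women of childbearing potential is analyzed at the site, as in Dose Escalation, and that a negative result must be seen before infusion.

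This adds one condition before dosing, and the text should say how it works:

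- result pending or indeterminate: infusion waits until a negative result is available;
- result positive: the existing withdrawal rule (8.3.4.1, 11.4.2.3) applies.

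All other central tests stay as they are.

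A lighter alternative is an early-draw window of up to 7 days, like that for CT, with review before dosing. It leaves a result up to 7 days old and may need an extra visit, so the site test is simpler.

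The cost is one sentence in each place, made by protocol amendment (15.2), which can be the next one due. Sites take on a local test and a short wait at each Day 1 visit, with an occasional brief dose delay. No laboratory safety analysis changes.
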